### **Unproven Interventions in Clinical Practice**

37. In the treatment of an individual patient, where proven interventions do not exist or other known interventions have been ineffective, the physician, after seeking expert advice, with informed consent from the patient or a legally authorised

representative, may use an unproven intervention if in the physician's judgement it offers hope of saving life, re-establishing health or alleviating suffering. This intervention should subsequently be made the object of research, designed to evaluate its safety and efficacy. In all cases, new information must be recorded and, where appropriate, made publicly available.

Disclaimer: ©2013 World Medical Association, Inc. All Rights Reserved. All intellectual property rights in the Declaration of Helsinki are vested in the World Medical Association. Previous permissions granted to publish or reproduce otherwise WMA policy don't apply to this version of the Declaration of Helsinki until January 1st, 2014. For further questions, please contact the WMA secretariat at [[contact]](mailto:[contact]).

## ABBREVIATIONS AND GLOSSARY

AE(s)	Adverse Event(s)
ALT	Alanine Aminotransferase
AST	Aspartate Aminotransferase
ATC	Anatomical Therapeutic Chemical
AUC	Area Under the Concentration-time Curve
BIMO	Bioresearch Monitoring
BSA	Body Surface Area
CI	Confidence Interval
Cl	Clearance
Cmax	Maximum Plasma Concentration
CPK	Creatine Phosphokinase
CPK-MB	Creatine Phosphokinase Isoenzyme MB
CrCl	Creatinine Clearance
CRF	Case Report Form
CRP	C-reactive Protein
CV	Coefficient of Variation
CYP	Cytochrome P450
D	Day
DL	Dose Level
DSBs	Double-strand Breaks
ECG	Electrocardiogram
ECHO	Echocardiogram
ECOG PS	Eastern Cooperative Oncology Group Performance Status
EDC	Electronic Data Capture
EOT	End of treatment
FDA	Food and Drug Administration
GCP	Good Clinical Practice
GGT	Gamma-glutamyltransferase
HR	Heart Rate
IC	Informed Consent
IC50	Half Maximal Inhibitory Concentration
ICH	International Conference on Harmonization
IEC	Independent Ethics Committee
INR	International Normalized Ratio
IRB	Institutional Review Board
i.v.	Intravenous
L	Liter
LDH	Lactate Dehydrogenase
LRB	Lurbinectedin
LVEF	Left Ventricular Ejection Fraction
MedDRA	Medical Dictionary for Regulatory Activities
Min	Minutes
Mg	Milligram
mL	Milliliter
MUGA	Multiple-gated Acquisition Scan
NA	Not Applicable
NCI-CTCAE	National Cancer Institute Common Toxicity Criteria
PD	Progressive Disease

PGt	Pharmacogenetic
PK	Pharmacokinetics
PN	Preferred Name
PS	Performance Status
PT	Preferred Term
q3wk	Every Three Weeks
R	Randomized
RBC	Red Blood Cells
RT	Reference-Test Sequence
RTSM	Randomization and Trial Supply Management
S	Sequence
SAE(s)	Serious Adverse Event(s)
SAP	Statistical Analysis Plan
SCLC	Small Cell Lung Cancer
SmPC	Summary of Product Characteristics
SOC	System Organ Class
T1/2	Terminal Half-life
TEAE(s)	Treatment-Emergent Adverse Events
TR	Test-Reference Sequence
ULN	Upper Limit of Normal
Vs.	Versus
Vss	Volume of Distribution at Steady State
WBC	White Blood Cells
WHO	World Health Organization
wk	Week(s)

## 1 STUDY RATIONALE

Lurbinectedin (PM01183) is a novel synthetic tetrahydroisoquinoline structurally related to ecteinascidins.

Lurbinectedin is a new chemical entity that binds the DNA leading to the formation of DNA double-strand breaks (DSBs). The binding to DNA is likely occurring in the minor groove region and induces apoptosis and delayed progression through the cellular phase S/G2. Lurbinectedin also induces the specific degradation of transcribing RNA Pol II in several human tumor cell lines.

In vitro, lurbinectedin demonstrated cytotoxic effects against a broad selection of tumor types with half maximal inhibitory concentration (IC50) values in the range of 1-10 nM. Although selectivity was also seen, a clustering of sensitive tumors has not been identified. Lurbinectedin also exhibited antitumor activity against different murine models of xenografted human-derived tumor types. Lurbinectedin has been tested as a single agent or in combination with different drugs in solid tumors; while antitumor activity in hematological tumors was deemed negligible, lurbinectedin has shown activity in different solid tumors; some of the most responsive tumor types were breast, small cell lung cancer (SCLC), ovarian and endometrial cancer.

Based on current clinical data, the toxicity of lurbinectedin is predictable, reversible and manageable. The most relevant toxicity is reversible myelosuppression with a nadir occurring in the middle of the second week after Day 1 infusion in an every-three-week cycle; overall, the incidence of febrile neutropenia is below 20% in all ongoing Phase II trials.

Lurbinectedin is extensively metabolized by the cytochrome P450 enzymes, primarily CYP3A4. Thus, potent inducers or inhibitors of this enzyme may alter the plasma concentrations of lurbinectedin. This study is designed to examine the pharmacokinetics (PK) and safety of lurbinectedin when co-administered with itraconazole, a strong CYP3A4 inhibitor, in comparison with lurbinectedin alone. The results of this study may be used to support future clinical studies in patients and prescribing information in future labeling.

A full rationale for the study may be found in the appropriate sections of the study's clinical protocol.

## 2 OVERALL STUDY DESIGN

This is a prospective, open-label, two-way crossover, phase Ib drug-drug interaction study in patients with advanced solid tumors.

The study will include a pre-treatment (screening) phase (within 14 days before the first lurbinectedin or itraconazole administration) followed by a treatment phase consisting of two lurbinectedin cycles, one cycle in combination with itraconazole and one cycle of lurbinectedin as single agent (in different order depending on the study sequence), and one additional third cycle of lurbinectedin as a single agent for patients who meet the continuation criteria and obtain a clinical benefit after the first two cycles, and then follow-up of adverse events if any.

Patients who meet the continuation criteria and obtain a clinical benefit according to the Investigator's criteria will have the opportunity to continue treatment under a Compassionate Use Agreement after the completion of the optional third study cycle.

[figure not shown]
Patients will be treated as outpatients. At the discretion of the Investigator, patients may be admitted to the study center on Day -1 or Day 1 and monitored, at least, until completion of the Day 1 PK blood sample collections.

Patients will receive a maximum of three cycles: two consecutive cycles of lurbinectedin, one cycle with and one cycle without itraconazole co-administration (in different order depending on the study Sequence 1 or Sequence 2 of treatment), followed by a third cycle with lurbinectedin alone (this last optional for patients with clinical benefit). Lurbinectedin will be administered as a 1-hour (-5/+20 min) i.v. infusion q3wk via a central or peripheral vein.

In the co-administration cycles, itraconazole will be administered orally once daily in the morning after breakfast during 12 consecutive days, self-administered at home from Day -4 (i.e., four days before lurbinectedin infusion) until Day 8 (i.e., seven days after lurbinectedin infusion), and supplied at the study center on Day 1, following recommendations at the Summary of Product Characteristics (SmPC). On Day 1 (i.e., the day of lurbinectedin infusion), itraconazole will be given immediately prior to starting the lurbinectedin infusion. In fact, itraconazole should be administered after obtain the itraconazole PK sample #1 and before the start of lurbinectedin infusion (-15 min to -1 min).

In case of lurbinectedin delay ( $\leq 2$  days), itraconazole could be administered during a maximum of 14 days.

This study will consist of two parts: Part A and B. The dose of lurbinectedin when given in combination with itraconazole for the initial three patients in Part A will be  $0.8 \text{ mg/m}^2$ , and in Part B is susceptible to be adjusted properly if deemed necessary based on exposure and safety experience in Part A. The dose of lurbinectedin during Parts A and B will be  $3.2 \text{ mg/m}^2$  for all patients when administered without itraconazole. If toxicity occurs, the appropriate intra-patient dose level (DL) reductions will be implemented in the subsequent cycle.

In Part A, three patients will be enrolled to Sequence 1 (TR: Test-Reference) and will receive itraconazole with lurbinectedin in Cycle 1 followed by two consecutive cycles of lurbinectedin alone (the last cycle being optional for patients with clinical benefit according to the Investigator's criteria).

Enrollment for Part A will be sequential. Once the first patient enrolled has completed Cycle 1 and Cycle 2, the second and the third patients could be enrolled simultaneously, after the evaluation of lurbinectedin total PK parameters, and if no unacceptable or life-threatening toxicities have occurred for this first patient. However, if toxicity occurs, the

appropriate dose reductions will be implemented with the second and third patients based on the PK and safety information of first patient.

The dose of lurbinecetin when given in combination with itraconazole for the initial three patients in Part A will be 0.8 mg/m^2. However, if lurbinecetin exposure in the first patient of Part A does not allow an adequate PK assessment, the lurbinecetin dose of the following patients may be increased accordingly.

Upon exposure and safety assessments in Part A, the dose of lurbinecetin to be co-administered with itraconazole in Part B can be readjusted accordingly. This decision will be made by the Sponsor and study Investigators, and will be documented and communicated to the Independent Ethics Committee/Institutional Review Board (IEC/IRB).

Therefore, the planned dose of lurbinecetin, when given with itraconazole for the remaining eight patients in Part B will be based on the acceptability of the PK and safety results from the first three patients in Part A. If the initial three patients do not experience adverse events (AEs) which might require a dose reduction, the dose of lurbinecetin may still be adjusted (based on the assumption of dose-proportional PK) to produce plasma lurbinecetin AUC values that are comparable to those when lurbinecetin is given in the absence of itraconazole. However, if toxicity occurs in the initial three patients in Part A, the appropriate dose-reduction of lurbinecetin will be implemented in Part B accordingly.

If the safety and PK data obtained from the three patients in Part A is deemed acceptable as defined in the protocol, Part B of this study will begin enrollment. Therefore, once Part A is completed, patients in Part B will be enrolled based on the review of the safety following completion of the first cycle of the previous patient(s), and will be randomized in a 1:1 ratio to Sequence 1 (as used in Part A) or Sequence 2 (RT: Reference-Test; lurbinecetin + itraconazole in Cycle 2).

In Part A, all patients will receive itraconazole plus lurbinecetin in Cycle 1 and lurbinecetin alone in Cycles 2 and 3 (this last cycle being optional).

In Part B, patients will be randomly assigned to the corresponding sequences:

- Sequence 1 (TR) (same used in Part A):
  - Cycle 1: Itraconazole + lurbinecetin
  - Cycle 2: Lurbinecetin alone
  - Cycle 3: Lurbinecetin alone (optional)
- Sequence 2 (RT):
  - Cycle 1: Lurbinecetin alone
  - Cycle 2: Itraconazole + lurbinecetin
  - Cycle 3: Lurbinecetin alone (optional)

Lurbinecetin will be administered to 11 evaluable patients for PK analyses and for a maximum of three cycles, while considered to be on the patient's best interest or until PD, unacceptable toxicity, intercurrent illness of sufficient magnitude to preclude safe continuation of the study, patient's refusal and/or non-compliance with study requirements, a protocol deviation with an effect on the risk/benefit ratio of the clinical

study, more than one lorbinecetin dose reduction due to AEs related to lorbinecetin (unless clear clinical benefit has been documented and always with the Sponsor's agreement) or any other reason at the physician's judgment that precludes lorbinecetin continuation.

If the patient responds to treatment after the first two cycles, treatment with lorbinecetin may continue outside this study under a Compassionate Use Agreement at the same dose based on Investigator's decision and upon agreement with the Sponsor. Then, the treating center must request authorization to the relevant Health Authorities and notify the Sponsor in due time. In order to avoid a treatment discontinuation, during the Compassionate Use Agreement authorization an additional third cycle with lorbinecetin is allowed.

All adverse events (AEs) will be graded according to the National Cancer Institute Common Terminology Criteria for Adverse Events (NCI-CTCAE) v.5. Treatment delays, dose reduction requirements and reasons for treatment discontinuation will be monitored throughout the study. The safety profile of patients will be monitored throughout the treatment and up to 31 days ( $\pm 10$  days) after the last lorbinecetin infusion (end of treatment, EOT), until the patient starts a new antitumor therapy or until the date of death, whichever occurs first. Any treatment-emergent AEs will be followed until recovery to at least grade 1 or stabilization of symptoms or until the start of a new antitumor therapy, until the continuation of treatment outside this study under a Compassionate Use Agreement or death, whichever occurs first. After treatment discontinuation, patients will be followed until resolution or stabilization of all toxicities, if any.

Patients will be evaluated at scheduled visits on three study periods: pre-treatment (screening), treatment (one cycle of lorbinecetin in combination with itraconazole and two as a single agent and the third cycle optional) and follow-up of adverse events if any.

### **3 PATIENTS EVALUABILITY CRITERIA**

Patients must fulfill all the inclusion/exclusion criteria to be eligible to participate in the study.

The study will include the following analysis population set definitions:

- The enrolled population is defined as all patients recorded in the database who are included in the trial, independently of whether they have received the study drug or not. Screening failure patients will not be considered as part of this population.
- The PK population will include all patients enrolled in Part A and B who have sufficient and interpretable PK parameters to calculate the non-compartmental PK parameters. Only the patients in Part B who have completed the two cycles and have sufficient and interpretable PK assessments will be included in the statistical comparison to assess the effect of itraconazole on the PK of lorbinecetin.
- The safety population will include all patients who received at least one dose of lorbinecetin. Patients who have received at least one dose of itraconazole but who did not receive any dose of lorbinecetin will be excluded from the safety population. The analysis of data from these patients will be performed separately (e.g., by means of narratives). The safety population will be used for all safety evaluations.

## 4 STUDY OBJECTIVES AND PHARMACOKINETIC PARAMETERS

### 4.1 *Objectives*

This clinical pharmacology study is designed to assess the impact of itraconazole co-administration on lurbinectedin PK parameters administered alone.

#### 4.1.1 *Primary*

- To assess the effect of itraconazole on lurbinectedin total plasma exposure in patients with advanced solid tumors.

#### 4.1.2 *Secondary*

- To assess the effect of itraconazole on lurbinectedin unbound plasma exposure.
- To assess the effect of itraconazole on lurbinectedin major metabolites (i.e., M1 and M4).
- To assess the effect of itraconazole on the safety profile of lurbinectedin.
- To collect and store a blood sample for germline DNA extraction for future pharmacogenetic (PGt) analysis of variations on genes that may influence exposure and response (i.e., disposition, metabolism and safety) to lurbinectedin.

### 4.1 *Endpoints*

#### 4.1.1 *Primary*

- Plasma dose-normalized  $C_{max}$  and  $AUC_{0-\infty}$  of lurbinectedin will be compared between Cycle 1 and Cycle 2. Pharmacokinetic analyses will be evaluated in plasma by standard non-compartmental methods, or population methods, if necessary.

#### 4.1.2 *Secondary*

- Differences in dose-normalized total  $AUC_{0-t}$  and  $C_{max}$  and in  $Cl$ ,  $V_{ss}$  and  $T_{1/2}$  of lurbinectedin between Cycle 1 and Cycle 2 will be explored.
- Differences in dose-normalized unbound  $AUC_{u,0-\infty}$ ,  $AUC_{u,0-t}$  and  $C_{u,max}$  and in  $CL_u$ ,  $V_{ss,u}$  and  $T_{1/2,u}$  of lurbinectedin between Cycle 1 and Cycle 2 will be explored.
- Differences in ratios between total  $AUC_{0-\infty}$ ,  $AUC_{0-t}$  and  $C_{max}$ , of main lurbinectedin metabolites relative to parent drug between Cycle 1 and Cycle 2 will be explored. Additional PK parameters will be calculated if deemed appropriate.
- Treatment safety, including AEs, serious adverse events (SAEs) and laboratory abnormalities will be graded according to the NCI-CTCAE v.5. Additionally, treatment compliance, in particular dose reductions requirements and/or treatment delays due to AEs, and reasons for treatment discontinuation will also be described. Patients will be evaluable for safety if they have received at least one partial or complete infusion of lurbinectedin.

- The presence or absence of PGt polymorphisms in genes relevant for lurbinectedin disposition (distribution, metabolism and excretion) from a single blood sample collected (only if written IC given) at any time during the trial (but preferably at the same time as the pre-treatments PK sample on Day 1 of Cycle 1), which will be stored to explain individual variability in main PK parameters in future analyses

## 5 SAMPLE CONSIDERATIONS

### 5.1 *Randomization*

A block randomization (1:1 ratio) will be performed only in Part B. Block randomization will be used to avoid bias in the assignment of patients to treatment sequence group, to increase the likelihood that known and unknown subject attributes (e.g., demographic and baseline characteristics) are evenly balanced across treatment sequence groups, and to enhance the validity of statistical comparisons across treatment sequence groups.

Patients must be replaced if they are not evaluable for the assessment of the primary endpoint (e.g., if they have not sufficient and interpretable PK parameters).

An evaluable patient for Part A should have completed sufficient study procedures until Day 8 of Cycle 1 (i.e., most itraconazole administration and PK assessments). For Part B, an evaluable patient for the main objective of the study (e.g., assessment of lurbinectedin PK) should have provided sufficient and interpretable PK parameters (e.g.,  $AUC_{0-t}$  should cover at least 80% of  $AUC_{0-\infty}$ ) of Cycle 1 and 2. Evaluable patients should have received the first two complete cycles regardless dose delays or reductions. For Part A and Part B, the compliance of itraconazole will be confirmed based on a patient's diary, the drug accountability and the expected individual plasma concentration at the steady state.

Randomization will be implemented in Medidata Rave RTSM for Part B of the study. A randomization list will be generated to randomly allocate patients to the sequence treatment. Additional randomization lists will be generated in case non-evaluable patients need to be replaced. Variable block sizes and allocation ratios will be used depending on the number of patients to be replaced in each case scenario in order to complete both sequence treatment groups while keeping balance across them. In order to achieve reproducible results, the seed used in the generation of each randomization list will be saved.

### 5.2 *Sample Size*

This study was designed to assess the potential effects of itraconazole on the PK of lurbinectedin in patients with advanced malignancies. The 90% CI will be used to help with the interpretation of the results. A sample size of eight patients was based on feasibility and clinical considerations. Based on previous studies, the intra-subject coefficient of variation (CV) of lurbinectedin PK parameters is estimated to be more than 30%. The precision (half-width) of the 90% CI for  $[(\text{lurbinectedin} + \text{itraconazole}) / \text{lurbinectedin alone}]$  comparison on the log-scale will extend 0.389 from the observed differences in means, assuming that the intra-subject CV around 40%. This half-width corresponds to a 90% CI in the range of 70% and 147% assuming the ratio of the means equal to unity for each PK parameter. This 90% CI will be used to help with the interpretation of the results.

## 6 STATISTICAL METHODOLOGY

The PK definitions and analysis plan will be described by the Pharmacology department in a separate document. The present SAP is focused on the statistical methodology for safety.

Safety analyses will consider treatment emergent AEs and SAEs, according to their relationship with study treatment, as well as analytical results, deaths and the reasons for treatment discontinuations, delays and/or dose reductions. All AEs and SAEs will be graded according to NCI-CTCAE v.5, and coded using the Medical Dictionary for Regulatory Activities (MedDRA).

Descriptive statistics will be used to characterize the profiles of drug-related AEs, drug-related deaths, SAEs, clinical laboratory data, drug-related delays and/or treatment discontinuations. Tables will be displayed by study part and sequence of treatment (Test/Reference or Reference/Test).

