#### **9.3.2 Safety**

All AEs will be graded according to NCI-CTCAE v.5.

Treatment-emergent adverse events (TEAEs) are any adverse event aggravated in severity from baseline or having their onset between the first dose of the study drug and 31-day ( $\pm 10$  days) after the last treatment dose, death or date of further therapy, whichever came first. AEs related to the study treatment or with unknown relationship occurring more than 31 days after the last dose were also taken into account as TEAEs.

Descriptive statistics will be used to characterize the profiles of drug-related AEs, drug-related deaths, SAEs, clinical laboratory data, drug-related delays and/or treatment discontinuations. Tables will be displayed by study part, sequence and treatment (Test or Reference).

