### **7.9 Subgroup Analyses**

Safety analysis will be done by study part and sequence treatment arm.

No other subgroup analysis is planned.

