## 11.2 Adverse Events (AEs)

This analysis will be carried out on evaluable patients for the safety population.

All adverse events tables will be listed by study part and sequence and differentiating by treatment (Test, Reference or both). Additional groups could be done (such as PM01183 alone or in combination) if required, and a sequential number will be added at the end of the table number.

AEs consisting of laboratory abnormalities (e.g., neutropenia) may be under-reported as AEs. Since these events are better evaluated using objective laboratory results, laboratory abnormalities will be discussed in Section 11.4.

The type of toxicity and worst grade or severity by cycle and by patient will be summarized according to System Organ Class (SOC) and Preferred Term (PT) as per the MedDRA dictionary. Subsequent grouping of similar or clinically related items might be appropriate at the time of the analysis. Tables will be organized by category of events using SOC and PT. Grades could be presented by separate or any other grouping at the time of the analysis.

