## 11.3 Serious Adverse Events and Deaths

### 11.3.1 Serious Adverse Events

This analysis will be carried out on evaluable patients for the safety population.

All serious adverse events tables will be listed by study part and sequence and differentiating by treatment (Test, Reference or both). Additional groups could be done (such as PM01183 alone or in combination) if required, and a sequential number will be added at the end of the table number.

The type of toxicity and worst grade or severity by cycle and by patient will be summarized according to System Organ Class (SOC) and Preferred Term (PT) as per the MedDRA dictionary. Subsequent grouping of similar or clinically related items might be appropriate at the time of the analysis. Tables will be organized by category of events using SOC and PT. Grades could be presented by separate or any other grouping at the time of the analysis.

If the number of SAEs are very low, these tables will not be presented and only listings will be shown.

Table 11.3.1.1 Treatment related† (or with unknown relationship) SAEs. Worst grade by treatment

Part A												
SOC/PT	T			R			All grades	Gr ≥ 3	Gr ≥ 4			
	All grades	Gr ≥ 3	Gr ≥ 4	All grades	Gr ≥ 3	Gr ≥ 4						
...												
Part B												
SOC/PT	S1			S2			T	R	T			
	All grades	Gr ≥ 3	Gr ≥ 4	All grades	Gr ≥ 3	Gr ≥ 4						
...												
Part A+B (S1)												
SOC/PT	T			R			Total					
	All grades	Gr ≥ 3	Gr ≥ 4	All grades	Gr ≥ 3	Gr ≥ 4	All grades	Gr ≥ 3	Gr ≥ 4			
...												

Notes: Percentage is based on number of patients by study part and sequence, when applicable.

† Related to both or luteinizing hormone-releasing hormone (LHRH) agonist or with unknown relationship.

Part A, patients assigned to Sequence 1; Part B, sequence assigned randomly.

S1, Sequence 1; S2, Sequence 2.

T, Test (ITZ+LRB); R, Reference (LRB alone).

Table 11.3.1.2 Lurbinectedin related† SAEs. Worst grade by treatment

Notes: Percentage is based on number of patients by study part and sequence, when applicable.

† Related to both or lurbinectedin or itraconazole or with unknown relationship.

Part A, patients assigned to Sequence 1; Part B, sequence assigned randomly.

S1, Sequence 1; S2, Sequence 2.

T, Test (ITZ+LRB); R, Reference (LRB alone).

Table 11.3.1.3 Itraconazole related† SAEs. Worst grade by treatment

	N(%)								
--	------	------	------	------	------	------	------	------	------

...

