## 11.4 Clinical Laboratory Evaluation

Tables will be listed by study part and sequence, however, additional groups could be done (such as PM01183 alone or in combination) if required, and a sequential number will be added at the end of the table number.

Grades could be presented by separate or any other grouping at the time of the analysis.

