### 11.4.1 Hematological Abnormalities

Table 11.4.1.1 Hematological abnormalities: Worst grade by treatment

Part A											
SOC/PT	T			R							
	All grades		Gr $\geq$ 3	Gr $\geq$ 4	All grades		Gr $\geq$ 3	Gr $\geq$ 4			
	N(%)	N(%)	N(%)	N(%)	N(%)	N(%)	N(%)	N(%)	N(%)	N(%)	
Anemia											
Leukopenia											
Lymphopenia											
Neutropenia											
Thrombocytopenia											
Part B											
SOC/PT	S1				S2						
	T		R		R		T				
	All grades	Gr $\geq$ 3	Gr $\geq$ 4	All grades	Gr $\geq$ 3	Gr $\geq$ 4	All grades	Gr $\geq$ 3	All grades	Gr $\geq$ 3	Gr $\geq$ 4
Anemia											
Leukopenia											
Lymphopenia											
Neutropenia											
Thrombocytopenia											
Part A+B (S1)										Total	
SOC/PT	T			R						Total	
	All grades	Gr $\geq$ 3	Gr $\geq$ 4	All grades	Gr $\geq$ 3	Gr $\geq$ 4	All grades	Gr $\geq$ 3	Gr $\geq$ 4	Total	
	N(%)	N(%)	N(%)	N(%)	N(%)	N(%)	N(%)	N(%)	N(%)	N(%)	
Anemia											
Leukopenia											
Lymphopenia											
Neutropenia											
Thrombocytopenia											

Notes: Percentage is based on number of patients by study part and sequence, when applicable.

† Related to both or lurbinectedin or itraconazole or with unknown relationship.

Part A, patients assigned to Sequence 1; Part B, sequence assigned randomly.

S1, Sequence 1; S2, Sequence 2.

T, Test (ITZ+LRB); R, Reference (LRB alone).

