### 11.4.3 Laboratory Values Over Treatment

Table 11.4.3.1 Shift of hematological abnormalities, worst grade per patient vs. baseline

Baseline grade	Worst grade per patient during treatment									
	Grade 1		Grade 2		Grade 3		Grade 4		Grade 5	
	N	%	N	%	N	%	N	%	N	%
Part A - S1 (TR)										
Anemia	G0									
	...									
	G4									
Leukopenia	G0									
	...									
	G4									
...	G0									
	...									
	G4									
Part B - S1 (TR)										
Anemia	G0									
	...									
	G4									
Leukopenia	G0									
	...									
	G4									
...	G0									
	...									
	G4									
Part B - S2 (RT)										
Anemia	G0									
	...									
	G4									
Leukopenia	G0									
	...									
	G4									
...	G0									
	...									
	G4									

Notes: Percentage is based on number of patients by study part and sequence, when applicable.

Part A, patients assigned to Sequence 1; Part B, sequence assigned randomly.

S1, Sequence 1; S2, Sequence 2; TR, test-reference; RT, reference-test.

If a low number of patients with grade  $\geq 3$  neutropenia or thrombocytopenia, the following table will be omitted and the information will be provided in a listing.

Table 11.4.3.2 Time course for neutrophils and platelets

	Part A		Part B		Part A+B		Total	
	S1 (TR)		S1 (TR)		S2 (RT)			
	N	Median (range)	N	Median (range)	N	Median (range)		
Neutropenia (Grade $\geq 3$ )								
Onset day								
Nadir day								
Recovery day								
Days to recovery								
Thrombocytopenia (Grade $\geq 3$ )								
Onset day								
Nadir day								
Recovery day								
Days to recovery								

Part A, patients assigned to Sequence 1; Part B, sequence assigned randomly.

S1, Sequence 1; S2, Sequence 2; TR, test-reference; RT, reference-test.

Table 11.4.3.3 Shift of biochemical abnormalities, worst grade per patient vs baseline

Baseline grade	Worst grade per patient during treatment									
	Grade 1		Grade 2		Grade 3		Grade 4		Grade 5	
	N	%	N	%	N	%	N	%	N	%
Part A - S1 (TR)										
ALT increase	G0									
	...									
	G4									
AST increase	G0									
	...									
	G4									
...	G0									
	...									
	G4									
Part B - S1 (TR)										
ALT increase	G0									
	...									
	G4									
AST increase	G0									
	...									
	G4									
...	G0									
	...									
	G4									
Part B - S2 (RT)										
ALT increase	G0									
	...									
	G4									
AST increase	G0									
	...									
	G4									
...	G0									
	...									
	G4									

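### The SAP's laboratory shift and time-course tables lack the Test/Reference split that Protocol 9.3.2 promises, and the only pooled split in SAP 11.2 to 11.4 is aliased with cycle order

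*SAP*

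**What the plan says.** Protocol 9.3.2 covers adverse events, deaths and clinical laboratory data, and states: "Tables will be displayed by study part, sequence and treatment (Test or Reference").

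The SAP describes itself in Section 6 as the safety methodology document, but is not consistent on this point:

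- Section 6: "Tables will be displayed by study part and sequence of treatment (Test/Reference or Reference/Test").
- Section 7.9: "Safety analysis will be done by study part and sequence treatment arm".
- Section 11.4, laboratory tables: "Tables will be listed by study part and sequence, however, additional groups could be done (such as PM01183 alone or in combination) if required".
- Section 11.2: "All adverse events tables will be listed by study part and sequence and differentiating by treatment (Test, Reference or both").
- Section 11.3.1: "All serious adverse events tables will be listed by study part and sequence and differentiating by treatment (Test, Reference or both").

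The shells follow the last two rules where adverse events are concerned. Laboratory worst grades are also split, as in "Table 11.4.1.1 Hematological abnormalities: Worst grade by treatment". The four tables in Section 11.4.3 are not: the two shift tables (11.4.3.1, 11.4.3.3) and the two time-course tables (11.4.3.2, "Time course for neutrophils and platelets", and 11.4.3.4 for AST and ALT) are laid out by part and sequence only.

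Section 11.5 offers a mixed model comparing the combination with lurbinectedin alone, with period and sequence as fixed effects, but makes it conditional on being applicable. Section 7.11 marks fixed or random effects models as not applicable.

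**The concern.** A secondary objective (Protocol 2.2, SAP 4.1.2) is the effect of itraconazole on the safety profile of lurbinectedin. Both documents name reversible myelosuppression as the drug's most relevant toxicity. A table that merges a patient's co-administration cycle with the single-agent cycle cannot address that objective, and Section 11.4.3 does this for the depth and timing of cytopenias.

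The pooled columns raise a separate problem. A reader wanting one Test column and one Reference column for adverse events finds only Part A+B (S1). Every patient there takes Test in Cycle 1, so a difference between the columns may reflect cycle order.

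An order effect is plausible on the protocol's own figures. Entry requires ANC of at least 2.0 and platelets of at least 120 (×10⁹/L, Protocol 4.1); re-treatment requires 1.5 and 100 (Table 7). Protocol 1.1.3.5 names baseline ANC and platelet count as the dominant covariates for neutropenia and thrombocytopenia. Dose reductions and secondary G-CSF, available after Cycle 1, could act the other way. Size and sign are therefore unknown.

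**Working it through.** The plan states no figure on this point to reproduce. The check has two parts.

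**1. Which safety tables carry treatment**

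| SAP tables | Test/Reference shown? |
|---|---|
| 11.2.1.1, 11.2.1.3 to 11.2.1.5, 11.2.1.8 (adverse events) | Yes: Part A, Part B S1, Part B S2, Part A+B (S1) |
| 11.3.1.1, 11.3.1.7 (serious adverse events) | Yes, same blocks |
| 11.4.1.1, 11.4.2.1 (laboratory worst grade) | Yes, same blocks |
| 11.4.3.1, 11.4.3.3 (laboratory shift) | No: part and sequence only |
| 11.4.3.2, 11.4.3.4 (laboratory time course) | No: part and sequence only |
| 11.5.1.1 (model-based comparison) | Yes, both sequences, any-event composites only, conditional |
| 11.7.1.1 to 11.7.1.3 (concomitant medication) | Yes, including Part B and Total |

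The column shells of 11.3.1.2 and 11.3.1.3 cannot be read in the available text and are left out. In the adverse event, serious adverse event and worst-grade shells, the Total, where shown, is not split.

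The shift tables take the worst grade per patient over all treatment. The time-course tables give a median and range; SAP 6.2 counts onset from the start of the cycle and includes all events. In both, Test and Reference cycles of the same patient enter one figure.

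**2. Aliasing in the pooled columns**

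Inputs: three Part A patients, all in Sequence 1 (Protocol 3.1); eight in Part B randomised 1:1 (Protocol 9.2), taken as 4 and 4. Sequence 1 over both parts then has 3 + 4 = 7 patients and Sequence 2 has 4. Only Cycles 1 and 2 are used, with all patients completing both.

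Code treatment as 1 for Test and cycle as 1 for Cycle 2. In Sequence 1, treatment = 1 - cycle for every patient.

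| Set | Test in Cycle 1 / Cycle 2 | Correlation of treatment and cycle | Rank of design |
|---|---|---|---|
| Part A+B (S1) | 7 / 0 | -1.0 | 2 of 3: not separable |
| Part B, S1+S2 | 4 / 4 | 0 | 4 of 4 |
| All A+B | 7 / 4 | -3/11 = -0.27 | 4 of 4 |

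The first design has an intercept, treatment and cycle; the others add sequence.

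To size this, assume no treatment effect and event risks p1 in Cycle 1 and p2 in Cycle 2. With *a* patients in Sequence 1 and *b* in Sequence 2,

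Test - Reference = [(a - b)/(a + b)] × (p1 - p2).

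| Assumed p1, p2 | S1 only (7, 0) | Part B (4, 4) | All A+B (7, 4) |
|---|---|---|---|
| 40%, 50% | -10 points | 0 | -2.7 points |
| 30%, 45% | -15 points | 0 | -4.1 points |
| 30%, 50% | -20 points | 0 | -5.5 points |
| 50%, 30% | +20 points | 0 | +5.5 points |

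These rates are assumptions, not figures from the documents. The S1-only column passes the whole cycle effect through as an apparent treatment difference, in either direction.

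**The case against.** A reader might infer from Sections 6 and 7.9 that the SAP has removed treatment from its safety displays altogether. The documents do not support that: Sections 11.2 and 11.3.1 require it, and the adverse event, serious adverse event and worst-grade laboratory shells deliver part by sequence by treatment, as the protocol asked. The incidence of neutropenia by treatment is already in Table 11.4.1.1.

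Nor does the SAP confine every Test/Reference comparison to Sequence 1. Section 11.5 adjusts for period and sequence, and the concomitant medication tables have Part B and Total columns by treatment. Pooling over sequence was never promised, and with about four patients per sequence a reader can add the Part B columns by hand. The first-in-human study reported no signs of cumulative toxicity (Protocol 1.1.3.1). If few patients have grade 3 or higher events, the time-course tables become listings.

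Most of this stands and limits the point. It does not answer the missing split in Section 11.4.3: Section 11.4 permits a treatment grouping only if required, whereas Protocol 9.3.2 makes it the rule. Section 11.5 covers only composites of any event, is conditional, and conflicts with Section 7.11. The aliasing holds whatever the cause or direction of an order effect.

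**Conclusion.** The point holds in three limited parts.

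- SAP Sections 6, 7.9 and 11.4 conflict with Protocol 9.3.2 and with SAP 11.2 and 11.3.1.
- Tables 11.4.3.1 to 11.4.3.4 cannot show any itraconazole effect on the grade shift, onset or recovery of neutropenia, thrombocytopenia or AST/ALT elevation.
- Within 11.2 to 11.4 the only pooled Test/Reference block is fully aliased with cycle order. Its Test column may also mix lurbinectedin doses, because the Part B co-administration dose can be changed after Part A. The order-balanced Part B sequences are shown side by side but not pooled.

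The first two are departures from the protocol or internal inconsistencies. Adding pooled Part B columns is an improvement, not a broken promise. The aliasing follows from the design; the 10 to 20 point range is illustrative.

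A reader might also infer that pooling Part B would isolate itraconazole's effect on safety. It would not. Lurbinectedin is planned at 3.2 mg/m² alone and starts at 0.8 mg/m² with itraconazole in Part A, with the Part B dose depending on Part A. Balancing order leaves dose tied to treatment.

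**What to change.** 1. Align SAP Sections 6, 7.9 and 11.4 with Protocol 9.3.2: part, sequence and treatment.
2. Split Tables 11.4.3.1 to 11.4.3.4 by Test and Reference for Cycles 1 and 2. Keep the study baseline for the shift tables. Cycle Day 1 pre-dose values are collected but should be at most a supplement: in Sequence 2 the Cycle 2 Day 1 value follows the itraconazole lead-in, so it is not an itraconazole-free baseline.
3. Add Part B (S1+S2) Test and Reference columns, limited to Cycles 1 and 2, to the by-treatment adverse event, serious adverse event and laboratory tables. Label the S1-only pool descriptive and confounded with cycle order. State where the optional Cycle 3 is counted, since the shells do not say whether it enters the Reference columns.
4. Reconcile Section 7.11 with Section 11.5, and say when the model will be fitted.
5. Footnote the by-treatment tables: lurbinectedin dose differs by design between Test and Reference.

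The cost is SAP text, shells and programming. No new data are needed, and Tables 11.7.1.1 to 11.7.1.3 already use a Part B Test/Reference layout.
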